7.1.3.1 Replacement policy

Patients lost to follow-up or withdrawing consent from the study without observed events for efficacy endpoints (e.g. PFS) will be censored for the data analysis and will not be replaced.

7.1.4 Withdrawal of consent

Patients may voluntarily withdraw consent to participate in the study for any reason at any time. Withdrawal of consent occurs only when a patient does not want to participate in the study any longer, and does not want any further visits or assessments, and does not want any further study related contact.

Novartis will continue to retain and use all research results that have already been collected for the study evaluation. All biological samples that have already been collected may be retained and analyzed at a later date (or as required by local regulations).

If a patient withdraws consent, the investigator must make every effort (e.g. telephone, e-mail, letter) to determine the primary reason for this decision and record this information.

Study treatment must be discontinued and no further assessments conducted.

Further attempts to contact the patient are not allowed unless safety findings require communication or follow up.

7.1.5 Follow up period

7.1.5.1 Safety follow up

All patients will be followed for AEs and SAEs for at least 30 days following the last dose of study treatment at the end of treatment phase.

At the end of this period, the investigator should assess and discuss with the patient any AE observed/concomitant medication taken since discontinuation of study treatment.

Patients whose treatment is permanently discontinued due to an AE (clinical or based on abnormal laboratory value) must be followed until resolution or stabilization of the event, whichever comes first. In case of an abnormal laboratory value, blood tests should be repeated until resolution or stabilization. Data collected should be added to the Adverse Events CRF and the Concomitant Medications CRF.

7.1.5.2 Post-treatment follow-up

All patients who discontinued treatment during the treatment phase for reasons other than death, lost to follow-up, pregnancy or PD (radiological as assessed by investigator) ([Section 7.1.3](#)) will continue tumor assessments as per [Table 7-1](#) (every 8 weeks) thereafter until PD (radiological as assessed by investigator), withdrawal of consent from tumor assessment, lost to follow-up or death. Once the patient ceases tumor follow-up, the reason for completion should be recorded on the End of Post Treatment Phase Disposition eCRF page.

7.1.5.3 Survival follow-up

All patients who had PD as per investigator assessment, have started a new anti-neoplastic therapy, and/or withdrew consent from further study assessments will subsequently be followed for survival information every 12 weeks until death, lost to follow-up or withdrawal of consent for survival follow-up. The investigator or his designee will collect this survival information and any new anti-neoplastic therapies for all patients until the final survival analysis.

Follow-up can be done via a phone contact. Antineoplastic therapies will be captured on the 'Antineoplastic therapies since discontinuation of study treatment' eCRF page following the last dose of the study treatment.

7.1.5.4 Lost to follow-up

For patients whose status is unclear because they fail to appear for study visits without stating an intention to withdraw consent, the investigator should show "due diligence" by contacting the patient, family or family physician as agreed in the informed consent and by documenting in the source documents steps taken to contact the patient, e.g. dates of telephone calls, registered letters, etc. A patient should not be considered lost to follow-up until due diligence has been completed. Patients lost to follow up should be recorded as such on the appropriate Disposition CRF.

7.2 Assessment types

7.2.1 Efficacy assessments

Tumor response will be assessed locally according to the Novartis guideline version 3.1 ([Appendix 2](#)) based on RECIST 1.1 ([Eisenhauer et al 2009](#)).

The imaging assessment collection plan is presented in [Table 7-2](#).

7.2.1.1 Baseline imaging (+/- photography) assessment

Imaging assessments will be performed at screening/baseline Day -28 to Day -1 prior to Cycle 1 Day 1.

Any imaging assessments already completed during the regular work-up of the patient within 28 days prior to start of treatment, including before signing the main study ICF, can be considered as the baseline images for this study.

Any imaging assessments obtained after first dose of study drug cannot be considered baseline images. The following assessments are required at screening/baseline:

- CT with IV contrast or MRI of chest and abdomen
- Whole body bone scan
- Brain CT with IV contrast or MRI scan
- Additional CT scan or MRI of other metastatic sites (e.g., neck, pelvis, etc.)
- Localized bone CT scan, MRI or x-ray (for any lesions identified on whole body bone scan not visible on chest/abdomen (and pelvis if applicable) CT scan or MRI)

- Photography (for any skin lesions) if clinically significant

If a patient is known to have a contraindication to CT intravenous (IV) contrast media or develops a contraindication during the trial, a non-contrast CT of the chest (MRI is not recommended due to respiratory artifacts, however if CT is not feasible per local regulations, MRI can be performed instead) plus a contrast-enhanced MRI (if possible) of the abdomen and pelvis (as applicable) should be performed.

A whole body bone scan should be performed per institutional standard of care for all patients to detect any skeletal metastases present [e.g., Tc-99 bone scan, whole body bone MRI, FDG-PET or sodium fluoride positron emission tomography (NaF PET)]. Localized CT, MRI or X-rays should be acquired for all skeletal lesions identified on the screening bone scan, which are not visible on the chest, abdomen and pelvis CT/MRI.

If clinically indicated, CT or MRI of other areas (neck, pelvis) of disease as appropriate should be performed.

Color photography, including a metric ruler to estimate the size of the lesion, must be acquired for all skin lesions present per instructions provided in the photography manual from the designated vendor.

Chest x-ray and ultrasound should not be used for lesion evaluation in this study.

7.2.1.2 Subsequent imaging for response assessment

Tumor evaluations as described in [Table 7-2](#) should be performed using the same imaging modality used at baseline, irrespective of study treatment interruption or actual dosing (see [Table 7-1](#)).

Tumor assessment for response determination will be made every 8 weeks starting from Day 1 of Cycle 3 (+/- 7 days window). **The 8 weeks interval should be respected regardless of whether treatment with LDK378 is temporarily withheld.**

Clinical suspicion of disease progression at any time requires a physical examination and radiological confirmation to be performed promptly rather than waiting for the next scheduled radiological assessment.

Each lesion that is measured at baseline must be measured by the same method (either same radiological method or by photography, including a metric ruler) and when possible, the same local radiologist/physician throughout the study so that the comparison is consistent. If an off-schedule imaging assessment is performed because progression is suspected, subsequent imaging assessments should be performed in accordance with the original imaging schedule.

Combined PET/CT may be used only if the CT is of similar diagnostic quality as a CT performed without PET, including the utilization of oral and IV contrast media. At the discretion of the Investigators, FDG-PET scans may be performed to document PD per RECIST 1.1 ([Appendix 2](#)).

Table 7-2 Imaging assessment collection plan

Procedure	Screening/Baseline	During Treatment/Follow-up
CT or MRI (Chest, Abdomen)	Mandated	every 8 weeks
Whole bone scan	Mandated	If clinically indicated
Brain CT or MRI	Mandated	Cycle 3 then every 2 cycle (i.e. every 8 weeks): only if positive at baseline or clinically indicated only if positive at baseline or clinically indicated.

 CT scan or MRI of other metastatic sites (e.g. neck, pelvis, etc) Localized bone CT scan, MRI or x-ray (for any lesions identified on the whole body bone scan that are not visible on the chest/abdomen CT scan or MRI) 	if clinically indicated	Cycle 3 then every 2 cycle (i.e. every 8 weeks): only if positive at baseline or clinically indicated only if positive at baseline or clinically indicated.

7.2.2 Safety and tolerability assessments

Safety will be monitored by the assessments described below as well as the collection of AEs at every visit. For details on AE collection and reporting, refer to [Section 8](#). Significant findings that were present prior to the signing of informed consent must be included in the relevant medical history/current medical conditions page on the patient's eCRF. Significant new findings that begin or worsen after informed consent must be recorded on the Adverse Event page of the patient's eCRF. All safety assessments at Cycle 1 Day1 have to be conducted prior to start of the first dose of LDK378, unless otherwise specified.

7.2.2.1 Physical examination

Physical examinations will include an examination of general appearance, skin, neck (including thyroid), eyes, ears, nose, throat, lungs, heart, abdomen, back, lymph nodes and extremities. Information about the physical examination must be present in the source documentation at the study center. For the assessment schedule refer to [Table 7-1](#).

Significant findings that were present prior to the signing of informed consent must be included in the Medical History page on the patient's eCRF. Significant new findings that begin or worsen after informed consent must be recorded on the Adverse Event page of the patient's eCRF.

7.2.2.2 Vital signs

Vital signs include body temperature, blood pressure and pulse measurements. Blood pressure (systolic and diastolic) and pulse should be measured after the patient has been sitting for five minutes.

For the assessment schedule refer to [Table 7-1](#).

7.2.2.3 Height and weight

Height in centimeters (cm) and body weight (to the nearest 0.1 kilogram [kg] in indoor clothing, but without shoes) will be measured. Height will be measured at screening only. For the assessment schedule for weight refer to [Table 7-1](#).

7.2.2.4 Performance status

WHO performance status will be assessed as per the assessment schedule (refer to [Table 7-1](#)). Assessment of WHO performance status ([Table 7-3](#)) will be performed within the time windows described above of the scheduled assessment, even if study treatment is being held. More frequent examinations may be performed at the investigator's discretion, if medically indicated.

Table 7-3 WHO performance status scale

Score	Performance Status
0	Fully active, able to carry on all pre-disease performance without restriction
1	Restricted in physically strenuous activity but ambulatory and able to carry out work of a light or sedentary nature, e.g. light housework, office work
2	Ambulatory and capable of all self-care but unable to carry out any work activities. Up and about more than 50% of waking hours
3	Capable of only limited self-care, confined to bed or chair more than 50% of waking hours
4	Completely disabled. Cannot carry on any self-care. Totally confined to bed or chair
5	Dead

7.2.2.5 Laboratory evaluations

Local laboratories will be used for the analysis of scheduled hematology, biochemistry and other blood specimens collected as part of safety monitoring (as detailed in [Table 7-1](#)). Dipstick urinalysis will also be performed locally. Laboratory values obtained during the Screening phase will be used to assess patient's eligibility. The time windows granted for laboratory evaluations are identical to the corresponding visit time windows for each visit (refer to [Section 7.1](#)).

Table 7-4 Local clinical laboratory parameters collection plan

Test Category	Test Name
Hematology	Hemoglobin, Platelets, Red blood cells, White blood cells with Differential (Basophils, Eosinophils, Lymphocytes, Monocytes, Neutrophils in percentage or absolute)
Chemistry	Albumin, ALT (SGPT), AST (SGOT), calcium, creatinine, creatinine clearance, total bilirubin, direct bilirubin (only if total bilirubin is \geq grade 2), blood urea nitrogen (BUN) or urea, magnesium, potassium, sodium, fasting glucose, phosphate(inorganic phosphorus), alkaline phosphatase, amylase, lipase, GGT
Urinalysis	Macroscopic Panel (Dipstick) (Color, bilirubin, Blood, Glucose, Ketones, pH, protein, specific gravity, urobilinogen) Microscopic panel (RBC, WBC, casts, crystals, bacteria, epithelial cells)
Coagulation	Pro-thrombin time (PT) and International normalized ratio (INR) or Quick Test
Pregnancy	At screening visit, serum pregnancy test At subsequent cycles, urinary pregnancy test.
Hormones (males only)	Testosterone (total and free), LH, Follicle-stimulating hormone (FSH)

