Isolated elevations of any grade	Maintain dose level
Total Bilirubin** (for patients with Gilbert Syndrome these dose modifications apply to changes in direct [conjugated] bilirubin only)	
Grade 1 ($>$ ULN and $\leq 1.5 \times$ ULN)	Maintain dose level with liver function test (LFTs)*** monitored as per protocol

Worst toxicity (CTCAE 4.03 Grade)*	Dose Modifications for LDK378
Grade 2 (> 1.5 and \leq 3.0 x ULN) with ALT or AST \leq 3.0 x ULN	Omit dose until resolved to \leq Grade 1, then: If resolved in \leq 7 days, then maintain dose level If resolved in > 7 days, then \downarrow 1 dose level
Grade 3 (> 3.0 and \leq 10.0 x ULN) with ALT or AST \leq 3.0 x ULN	Omit dose until resolved to \leq Grade 1, then: If resolved in \leq 7 days, \downarrow 1 dose level If resolved in > 7 days discontinue patient from LDK378
Grade 4 (> 10.0 x ULN)	Permanently discontinue patient from LDK378
AST or ALT	
Grade 1 (> ULN and \leq 3.0 x ULN)	Maintain dose level with LFTs*** monitored per protocol
Grade 2 (> 3.0 and \leq 5.0 x ULN) without total bilirubin elevation to > 2.0 x ULN	Maintain dose level with LFTs*** monitored per protocol
Grade 3 (> 5.0 and \leq 20.0 x ULN) without total bilirubin elevation to > 2.0 x ULN	Omit dose until resolved to \leq Grade 1, then \downarrow 1 dose level
Grade 4 (> 20.0 x ULN) without total bilirubin elevation to > 2.0 x ULN	Omit dose until resolved to \leq Grade 1, then \downarrow 1 dose level
AST or ALT and concurrent total bilirubin	
AST or ALT > 3.0 x ULN with total bilirubin > 2.0 x ULN in the absence of cholestasis or hemolysis	Permanently discontinue patient from LDK378 Refer to Section 6.3.4.2 for additional follow-up
PANCREATIC	
Amylase and/or lipase elevations (in the absence of clinical symptoms)	
Grade 1 (> ULN and \leq 1.5 x ULN)	Maintain dose level
Grade 2 (> 1.5 - 2.0 x ULN)	Maintain dose level
Grade \geq 3 (> 2.0 x ULN)	Omit dose until resolved to \leq Grade 1, then \downarrow 1 dose level
Note: Withhold LDK378 for acute onset of new or progressive unexplained abdominal symptoms, such as severe pain or vomiting; perform diagnostic procedures (e.g., abdominal CT scan or ultrasound) to exclude pancreatic pathology.	

Worst toxicity (CTCAE 4.03 Grade)*	Dose Modifications for LDK378
RENAL	
Serum creatinine	
Grade 1 (>1 and ≤ 1.5 x baseline; > ULN and ≤1.5 x ULN)	Maintain dose level

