6.3.4.2 Guidelines for the follow-up of liver laboratory abnormalities

In patients with any clinically relevant laboratory liver abnormality, as defined below, hepatic toxicity monitoring must include **ALL** of the following live function tests (LFTs): albumin, ALT, AST, total bilirubin (fractionated if total bilirubin $> 2.0 \times$ ULN), alkaline phosphatase and GGT).

Note: for patients with Gilbert Syndrome, total and direct bilirubin must be monitored, but intensified monitoring applies to changes in direct bilirubin only.

In case of any occurrence of ALT/AST/total bilirubin increase to grade 2 the LFTs must be monitored weekly (or more frequently if clinically indicated) until the event resolves to \leq grade 1. Thereafter monitoring must be continued every other week (or more frequently if clinically indicated) for two additional cycles (e.g. 8 weeks). If there is no recurrence of grade 2 ALT/AST/total bilirubin elevations during this period, subsequent monitoring must be performed every 4 weeks. For patients with liver metastasis and grade 2 AST/ALT at baseline, increased monitoring is required for grade 3/4 AST/ALT; follow guidelines for grade 3 or 4 AST/ALT.

In case of any occurrence of ALT/AST/ total bilirubin increase to grade 3 or 4, LFTs must be monitored weekly (or more frequently if clinically indicated) until the event resolves to \leq grade 1 (or to baseline). Thereafter monitoring must be continued every other week (or more frequently if clinically indicated) for four additional cycles (e.g. 16 weeks). If there is no recurrence of \geq grade 2 ALT/AST/ total bilirubin elevations during this period, subsequent monitoring must be performed every 4 weeks.

Patients who discontinue study treatment due to liver toxicity must be monitored weekly (or more frequently if clinically indicated) until the event resolves to \leq grade 1 or stabilization occurs (no CTCAE grade change over 4 weeks). Refer to [Table 6-4](#).

Patients with transaminase increase combined with total bilirubin (TBIL) increase may be indicative of potential drug-induced liver injury (DILI), and should be considered as clinically important events.

The threshold for potential DILI may depend on the patient's baseline AST/ALT and TBIL value; patients meeting any of the following criteria will require further follow-up as outlined below:

- For patients with normal ALT and AST and TBIL value at baseline: AST or ALT > 3.0 x ULN combined with TBIL > 2.0 x ULN

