7.2.2.5.2 Clinical chemistry

Blood chemistry assessments of the parameters listed in [Table 7-4](#) will be tested as per the schedule of assessments ([Table 7-1](#)).

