Local laboratories will be used for laboratory evaluations in this study. Laboratory data will be classified (by Novartis Oncology Statistical Programming personnel) into CTC grades according to the CTCAE version 4.03. For all reports, CTC grade is always obtained on the converted measurement in SI unit. Grade 5 will not be used. The CTC grade 0 will be assigned as below in different scenarios:

1. For laboratory parameters defined by criteria based on normal range only, a CTC grade of 0 will be assigned when the value is within normal limits.
2. For laboratory parameters whose grade is defined by criteria based on normal range and absolute values (e.g., platelet count decrease). A CTC grade of 0 will be assigned when the value is within normal limits.
3. For laboratory parameters whose grade is defined by criteria based on normal range and the change from baseline value with no other associated clinical criteria such as concomitant medication (e.g., creatinine increased), the following will be applied. For the grading of baseline value and for the grading of post-baseline values with missing baseline value, the grade will be derived using the criteria based only on the normal range as per CTCAE version 4.03. A CTC grade of 0 will be assigned when the post-baseline value is \leq ULN (for hyper) or \geq LLN (for hypo).

Laboratory parameters for which a grading does not exist will be classified into low/normal/high group by means of laboratory normal ranges.

As described previously, laboratory summary tables will include only laboratory assessments collected during the on-treatment period. Shift tables may use data from pre-treatment period for baseline calculations. The following summaries will be produced separately for the hematology and biochemistry (including hormones) laboratory data (by laboratory parameter):

- Shift tables using CTC grades to compare baseline to the worst post-baseline value for laboratory parameters with CTC grades.
- Shift tables using low, normal, high (as well as low and high combined) classifications to compare baseline to the worst post-baseline value for laboratory parameters where CTC grades are not defined.

The laboratory parameters listed in [Table 2-3](#) will be summarized as above stated. For bi-directional parameters, both hyper and hypo summaries will be presented.

Table 2-3 Laboratory parameters for summaries

Category	Parameter with CTC grades	Parameter without CTC grades

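### Table 7-4 takes direct bilirubin only when total bilirubin is grade 2 or higher, with no Gilbert exception, which conflicts with the Gilbert rules in Table 6-3 and 6.3.4.2 and leaves the SAP's direct-bilirubin shift table almost without baselines

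*Protocol*

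**What the plan says.** **Collection.** Protocol 7.2.2.5, Table 7-4, has a chemistry list in which most analytes are unconditional. Direct bilirubin is conditional: "direct bilirubin (only if total bilirubin is" grade 2 or higher. Section 7.2.2.5.2 makes this list the operative one: "Blood chemistry assessments of the parameters listed in" Table 7-4 are tested according to Table 7-1.

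**Dose rules.** In protocol 6.3.3, Table 6-3, the Total Bilirubin heading carries a qualifier: "for patients with Gilbert Syndrome these dose modifications apply to changes in direct [conjugated] bilirubin only". Grade 2 in that block means above 1.5 and up to 3.0 x ULN. The AST or ALT rows, and the row combining AST or ALT with concurrent total bilirubin, carry no such qualifier.

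**Monitoring.** Protocol 6.3.4.2 states: "for patients with Gilbert Syndrome, total and direct bilirubin must be monitored, but intensified monitoring applies to changes in direct bilirubin only". The same section describes the liver panel as including "total bilirubin (fractionated if total bilirubin" exceeds 2.0 x ULN.

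**Eligibility.** Inclusion criterion 10 caps total bilirubin at 1.5 x ULN. Gilbert patients may instead enter with total up to 3.0 x ULN or direct up to 1.5 x ULN.

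**Analysis.** SAP Table 2-3 lists direct bilirubin among biochemistry parameters without CTC grades. SAP 2.8.2 gives such parameters this output: "Shift tables using low, normal, high (as well as low and high combined) classifications to compare baseline to the worst post-baseline value".

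**The concern.** A dose rule stated in terms of a change in an analyte needs that analyte at baseline and at follow-up. In Gilbert patients the Total Bilirubin rows of Table 6-3 are stated in terms of direct bilirubin, yet the collection table withholds that test until total bilirubin reaches grade 2. If sites work from Table 7-4, a change in direct bilirubin in a Gilbert patient with a lower total may not be seen. Hepatotoxicity is an adverse event of special interest in protocol 8.1.3, so the collection plan and the dose rules should agree.

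The reporting problem is separate. A shift table compares each patient's baseline with the worst later value. If the baseline is not collected for most patients, and later values exist mainly because total bilirubin rose, the table describes a small selected group. Nothing in its planned layout would show this.

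**Working it through.** No power or sample-size figure is at issue. The check compares thresholds and then counts.

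**Step 1: the Table 7-4 trigger.** Grade 2 total bilirubin in Table 6-3 starts above 1.5 x ULN, so Table 7-4 calls for direct bilirubin only when total > 1.5 x ULN.

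**Step 2: Gilbert patients below the trigger.** Take a Gilbert patient with total ≤ 1.5 x ULN.

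| Source | Direct bilirubin in this patient |
|---|---|
| Table 7-4 | not taken |
| Table 6-3, Total Bilirubin rows | rule acts on its change |
| Section 6.3.4.2 note | must be monitored |
| Inclusion criterion 10 | not needed: total ≤ 1.5 x ULN already meets the 3.0 x ULN limb |

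Eligibility does not rescue the baseline. A Gilbert patient who needs the direct limb has total > 3.0 x ULN, which is already above the Table 7-4 trigger.

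**Step 3: the two fractionation thresholds.** Table 7-4 uses > 1.5 x ULN and the 6.3.4.2 panel uses > 2.0 x ULN. Since 1.5 < 2.0, every patient above the 6.3.4.2 threshold is also above the Table 7-4 one. The texts differ only for totals above 1.5 and up to 2.0 x ULN, where Table 7-4 takes the fraction and the panel does not ask for it.

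**Step 4: baselines for the SAP shift table.** A non-Gilbert patient is eligible only if screening total ≤ 1.5 x ULN, while the trigger is > 1.5 x ULN. The two cannot hold together, so Table 7-4 calls for no screening direct bilirubin in that patient. The documents do not give the number of Gilbert patients, g. Assuming g among the planned 20, at most g patients have a screening value, so at least 20 − g have none:

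| Assumed g | At least without a screening value | Percent, (20 − g)/20 |
|---|---|---|
| 0 | 20 | 100% |
| 1 | 19 | 95% |
| 2 | 18 | 90% |
| 3 | 17 | 85% |
| 4 | 16 | 80% |

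These counts are minimums because a Gilbert patient with total ≤ 1.5 x ULN also has no value under Table 7-4.

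**Step 5: post-baseline values.** The same trigger applies during treatment, so later values under Table 7-4 come from visits with total at grade 2 or higher. SAP 2.8.2 names a missing category in its total bilirubin, ALT, AST and ALP shift tables, but not in the low/normal/high tables that hold direct bilirubin.

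**The case against.** The strongest reply is that the protocol does ask for the test. Section 6.3.4.2 says "for patients with Gilbert Syndrome, total and direct bilirubin must be monitored", and a site could treat this as a specific instruction that overrides the general line in Table 7-4. This reply has force: it rules out saying that the protocol never requires direct bilirubin in Gilbert patients. What remains is a contradiction. The note sits under a paragraph on patients with a clinically relevant liver abnormality. Read narrowly, it does not reach a Gilbert patient with a low total and no other abnormality. Read broadly, it cannot stand beside the restriction in Table 7-4.

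Other replies also narrow the point:

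- A reader might infer that every bilirubin-related dose rule fails in Gilbert patients. The documents do not support that. The qualifier covers only the Total Bilirubin rows; the AST or ALT and concurrent-bilirubin rows use total bilirubin, which Table 7-4 collects unconditionally.
- A reader might infer that the two thresholds leave patients unfractionated. They do not, because following Table 7-4 always satisfies 6.3.4.2.
- A reader might infer that baseline is missing in every non-Gilbert patient. That is slightly too strong. SAP baseline is the last assessment on or before the first dose, so a rise to grade 2 between screening and Day 1 could supply one, and sites may measure direct bilirubin anyway.
- Only the antineoplastic-therapy and survival rows of Table 7-1 could be read, so a direct-bilirubin row or footnote there cannot be excluded.
- The SAP already plans a full laboratory listing, and direct bilirubin is not among its named liver tests of interest, so little is lost if the shift table is dropped.

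An example in concentration units would need assumed upper limits of normal, and an assumption that the Table 6-3 multiples carry over to the direct fraction. The documents give neither, and the conclusion does not use one.

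**Conclusion.** The point holds in a limited form. Table 7-4 as written conflicts with the Total Bilirubin rows of Table 6-3 and with the Gilbert note in 6.3.4.2. A site following Table 7-4 can lack both the value and the baseline for a Gilbert patient whose total is below grade 2. The number affected is unknown and, among about 20 patients, may be zero. The differing fractionation thresholds are a minor inconsistency.

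On the SAP side, eligible non-Gilbert patients would ordinarily have no baseline direct bilirubin under the plan. The shift table would then rest on few baselines and on later values selected for a raised total. The 80% to 100% range assumes 0 to 4 Gilbert patients, collection exactly as in Table 7-4, and no rise to grade 2 before the first dose.

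The effect is confined to safety monitoring and one safety table. ORR and the other efficacy endpoints do not use this analyte.

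**What to change.** **Protocol.** The sponsor should reconcile Table 7-4, the Total Bilirubin rows of Table 6-3 and section 6.3.4.2, with Table 7-1 checked at the same time, so that they agree on when direct bilirubin is measured, in Gilbert patients in particular. The grade 2 and 2.0 x ULN fractionation thresholds should be aligned in the same edit. Which rule should prevail is a clinical decision and is not proposed here.

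**SAP.** Choose one of two options:

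1. Remove direct bilirubin from the shift tables and rely on the listing of all laboratory data already planned in 2.8.2.
2. Keep the table but restrict it to patients with a baseline value, show the numbers tested and missing, and add a footnote that post-baseline values are taken mainly when total bilirubin is grade 2 or higher.

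**Cost.** Protocol wording and one SAP output. If the reconciliation leads to more testing, it adds one analyte from blood already drawn, in what are likely to be few patients.
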